8.2 SAFETY AND OTHER ASSESSMENTS

8.2.1 SAFETY

1. A suicide questionnaire previously used in IRBs #14-0600 and #14-1622 will be used at each session of this study. This questionnaire tracks suicidal ideation and behavior. Participants will be asked to answer whether they have had any thoughts of hurting themselves within the past 24 hours (suicidal ideation, SI) and whether they have hurt themselves within the past 24 hours (suicidal behavior, SB). If a participant admits to experiencing either SI or SB their participation will be stopped immediately and their primary mental health care provider or family physician will be contacted. In the case that they do not see anyone for their depressive symptoms, [name] will assist the participant in seeking medical care
2. The structural MRI to be used for source localization during EEG analysis will be conducted prior to randomization. The results of the T1 weighted sMRI will be reviewed by [name] for incidental findings of malignancy. If any are found, the study team will disqualify patient from study participation and will facilitate contact with providers for medical care per [name] recommendations. Patients will complete the provided MRI screening form provided by the Biological Research Imaging Center (BRIC) prior to the sMRI screening visit.
3. A stimulation adverse effects questionnaire will be administered at the end of each stimulation session. This questionnaire will be used as a safety measure and to collect data on participant experience. This questionnaire has been used in all our previous tACS studies.

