9.4.4 SAFETY ANALYSES

Safety will be assessed with a suicide questionnaire, the Columbia-Suicide Severity Rating Scale (C-SSRS), an adverse effects questionnaire, and the Young Mania Rating Scale (YMRS).

The suicide questionnaire is used as a screening to assess increase in suicidal ideation (SI) or suicidal behavior (SB). If a participant's responses indicate SI or SB, the participant will be contacted and an acute assessment will be completed if necessary by [name]. Any verified increases in suicidal ideation will be described in counts/percentages and compared between groups using chi-square tests.

The adverse effects questionnaire will be administered following every stimulation session, for a total of 5 administrations per participant. The adverse effects questionnaire inquires about 14 possible adverse effects associated with electrical stimulation, rated on a scale of 1 (absent) to 4 (severe). Paired t-tests

with random effect "participant" will be calculated per adverse effect to determine if there are any differences in adverse effect severity between groups (sham/placebo, alpha-tACS, theta-tACS). Severity per adverse effect will be described with mean and standard deviation.

The Young Mania Rating Scale (YMRS) will be used to assess any development of mania over the course of treatment. A YMRS score of greater than 12 indicates the possible development of a manic episode. Any participant who scores greater than 12 on the YMRS will be assessed by [name]. Any verified manic episode will be described in counts/percentages and compared between groups using a chi-square test.

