9.4.6 PLANNED INTERIM ANALYSES

Blinded interim descriptive analyses on the safety measures (blinded adverse effects, responses to the suicide assessment, cognitive scores from the cognitive battery, as well as any adverse events) will be provided to the Data Safety and Monitoring Board (DSMB) every 6 months.

Additionally, in the event of 2 SAEs (if enrollment is less than 10 subjects), possibly or definitely associated with the study intervention, the study will be suspended and the DSMB will be notified. If enrollment is more than 10 subjects, in the event of the equivalent SAEs to 20% of study enrollment, possibly or definitely associated with the study intervention, the study will be suspended and the DSMB will be notified.

If there is reason to view unblinded information, the DSMB will directly receive the list of participants' identification numbers from [name]. Participant identification number will be displayed in a table according to the three arms of the study; however, the specific treatment of each arm will not be disclosed. This will allow the DSMB to compare the three intervention groups.

There are no other planned interim analyses.

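### The only planned between-arm suicidality result is verified ideation: suicidal behaviour, the C-SSRS and unverified answers have no final by-arm analysis, and no safety population is defined

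*Combined protocol and SAP*

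**What the plan says.** Section 9.4.4 opens with its instruments: "Safety will be assessed with a suicide questionnaire, the Columbia-Suicide Severity Rating Scale (C-SSRS"), followed by the adverse effects questionnaire and the YMRS. It then gives the questionnaire a double purpose: "The suicide questionnaire is used as a screening to assess increase in suicidal ideation (SI) or suicidal behavior (SB"). After a positive answer of either kind the participant is contacted, and "an acute assessment will be completed if necessary". The analysis is one sentence: "Any verified increases in suicidal ideation will be described in counts/percentages", with a chi-square comparison between the groups. The section does not say what makes an increase verified, when an assessment is necessary, or which participants are analysed.

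Section 8.2.1 gives the questionnaire at each session. It asks about thoughts of self-harm over the past day and, separately, "whether they have hurt themselves within the past 24 hours (suicidal behavior, SB"). Section 8.1.3 schedules the C-SSRS at screening, baseline, Day 5 and both follow-up visits. Section 9.4.6 sends "responses to the suicide assessment" to the DSMB every six months as blinded descriptive data. Section 9.3 fixes a per-protocol dataset of participants who complete all five stimulation days and defines no other population.

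**The concern.** The comparison is narrower than the data collected for it. The questionnaire separates ideation from behaviour, yet the graver answer has no line of its own in the final result. The C-SSRS is introduced as a safety measure and then not mentioned again in the section. An ideation answer enters only after passing a condition that is not defined.

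This matters more than usual here. Section 2.3.1 says that theta-tACS could in theory worsen depression. The same section supports the safety of the method with a by-arm count from a similar depression study: four sham participants with more suicidal thoughts, one of them with intent, against none on tACS. Followed as written, this trial's plan would not guarantee a report at that level of detail.

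**Working it through.** The plan states no event rate, power or sample size for suicidality, so there is no figure to reproduce. The check is a comparison of sections, followed by an illustration.

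**Step 1. What is collected against what is analysed by arm at the end.**

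| Item | Collected | Final by-arm analysis in section 9 |
|---|---|---|
| Ideation answer | each session (8.2.1) | verified increases only, chi-square (9.4.4) |
| Behaviour answer | each session (8.2.1) | none named |
| C-SSRS | screening, baseline, Day 5, both follow-ups (8.1.3) | none named |
| AEs and SAEs | from consent to 7 or 30 days after the 3-month follow-up (8.3.4) | none named |

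The last row matters because an AE table by arm could have picked up suicidal behaviour indirectly. No such final analysis is described.

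**Step 2. Path of an event during stimulation week.** Under 8.2.1 an admission of ideation or behaviour stops participation at once. Under 7.2 a participant who received only part of the intervention is replaced. Under 9.3 only five-day completers are analysed. Taken literally, a participant who answers positively before completing the fifth session leaves the dataset, whether or not the event is verified. Section 7.1 still follows participants who withdraw from the intervention to week 4 with the suicide questionnaire, so data would exist with no analysis to receive them. Events at the follow-up visits are not affected by this path.

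**Step 3. Illustration with assumed counts.** Inputs from the plan: 45 analysable participants (9.3) at 1:1:1, so n = 15 per arm; a chi-square test (9.4.4); a 0.05 threshold (9.4.1). Assumed: four positive participants, all in one arm. This borrows the count from the similar depression study in 2.3.1 for scale only. How many would be verified is unknown, so every value of k, the number counted, is shown.

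With k events in one arm and none in the other two, the Pearson statistic reduces to X² = 6kn/(3n − k). On 2 degrees of freedom, p = exp(−X²/2). The expected event count per arm is k/3. The exact (Fisher-Freeman-Halton) p-value for k = 2 to 4 is 3·C(n,k)/C(3n,k); for k = 1 it is 1.

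| k | X² | chi-square p | expected events per arm | exact p |
|---|---|---|---|---|
| 4 | 360/41 = 8.78 | 0.012 | 1.33 | 4095/148995 = 0.028 |
| 3 | 270/42 = 6.43 | 0.040 | 1.00 | 1365/14190 = 0.096 |
| 2 | 180/43 = 4.19 | 0.123 | 0.67 | 315/990 = 0.318 |
| 1 | 90/44 = 2.05 | 0.360 | 0.33 | 1.0 |

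Arm size changes little. At 20 per arm the chi-square p is 0.014 for k = 4 and 0.362 for k = 1; at 24 per arm it is 0.0145 and 0.363. With so few events, one or two classification decisions settle the result. The expected counts are also far too small for the chi-square approximation.

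**The case against.** Several points on the other side are sound.

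- **Verification is a reasonable idea.** Eligibility admits HDRS17 suicide-item scores below 3, so some low-level suicidality may be present at entry. Counting every positive answer could mix unchanged ideation with new events. Mania is handled in the same confirmed-event way in 9.4.4. This stands, and it is why the fix keeps verified status and adds change from baseline.
- **A reader might infer that the discretionary assessment is the gate.** That is the natural reading of the preceding sentence, but the text does not say so. Verification could come from the contact with the participant or from the C-SSRS. What can be shown is that the term is undefined.
- **A reader might infer that behaviour events disappear entirely.** They do not have to. A participant with suicidal behaviour may also be recorded with increased ideation, the event may enter the AE or SAE records, and the DSMB sees the responses and may be shown masked arms. What is missing is a planned final count and comparison by arm.
- **A reader might infer that the trial would report no difference between arms.** Section 9.4.1 requires non-significant tests to be reported as inconclusive.
- **A reader might infer bias towards one arm, or a contradiction between interim and final counts.** Participants and researchers are blinded, and nothing suggests that verification would differ by arm. Blinded interim listings and a final confirmed-event comparison can legitimately differ.
- **The example is assumed.** With two to four events any reclassification moves p, so the table shows fragility and does not estimate the loss.

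None of this supplies the missing by-arm analysis of behaviour and the C-SSRS, the definition of verified, or a safety population.

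**Conclusion.** The point holds as a gap in the planned safety result. Section 9.4.4 compares only verified increases in ideation, and no other section plans a final by-arm analysis of suicidal behaviour, the C-SSRS or AEs. Sections 8.2.1 and 9.3 together could also remove verified events that occur in stimulation week. That second part rests on applying the per-protocol dataset to safety, which is the literal reading because 9.4.4 names no population of its own.

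The size cannot be derived from the documents. Under the assumed four-in-one-arm case with 15 per arm, the planned test runs from p = 0.012 with all four counted to p = 0.36 with one counted. The documents do not support a claim of total undercounting of behaviour, of a false report of no difference, or of a filter that favours an arm.

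**What to change.** In 9.4.4, report by arm, in all randomised participants who received any stimulation, the number with:

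1. any positive ideation answer after the first stimulation, flagging those new or increased from a named baseline reading;
2. any positive behaviour answer after the first stimulation;
3. C-SSRS worsening from baseline.

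Count each participant once per row. Define verified, and show verified cases as a subset of each row and not as the condition for entry. Replace the chi-square test with an exact test, or give descriptive intervals only.

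Sections 7.1, 8.2.1 and 9.4.4 differ on what a positive answer triggers: an acute assessment that decides discontinuation, immediate stopping, or contact with an assessment where needed. They must be reconciled, because the rule determines who remains under observation. No clinical rule is proposed here.

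The cost is wording and a few table rows; the scheduled assessments already supply the data. One limit is that 7.1 does not list the C-SSRS among the assessments kept after withdrawal from the intervention, so row 3 should state the number assessed. Some counted answers will prove clinically unimportant, which the verified and change-from-baseline columns will show.

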Risk of Injury and Discomfort: The side effects of tACS are mild and transient; in fact, low intensity transcranial current stimulation, such as tACS, has been used for several years without any report of serious side effects ([name] & McCormick, 2010). Furthermore, this stimulation mode has nothing to do with electroconvulsive therapy that applies many orders of magnitude higher stimulation current. Rather, transcranial current stimulation is so weak that it does not cause super-threshold activation of neurons (Khan, Khan, Shankles, & Polissar, 2002). However, tACS does have some mild side effects, such as transient mild tingling, burning, or itching under the electrode sites. In the first part of this study, participants from all three groups reported either absent or mild side effects and there was no difference between the groups with the exception of "flickering lights" (or phosphene, $p = 0.014$) (Alexander et al., 2019). In order to monitor these, we will be administering an adverse effects stimulation questionnaire after each stimulation session to determine whether these effects were experienced and at what intensity. Research personnel present during these sessions will also check in with the participant periodically during the stimulation to see whether they are comfortable. If participant is experiencing severe discomfort (as determined by the adverse effects questionnaire or by self-report), the stimulation will be immediately stopped.

Risks associated with emotional distress in case of incidental findings on structural MRI or a false positive pregnancy test.

Risks associated with venous blood draw include minimal discomfort and/or bruising. Infection, excess bleeding, clotting, and fainting are also possible, although unlikely.

Patients experiencing depression have a higher risk of suicide. We have no evidence that our treatment paradigms will in any way increase this likelihood. In a similar study in patients with major depressive disorder (MDD), 4 participants in the sham/placebo stimulation group experienced an increase in suicidal thoughts and only one of those 4 participants reported suicidal intent. No participants who

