9.2 SAMPLE SIZE RATIONALE

At this point in time, no clinical trial has been completed using tACS to treat SLE. However, the Carolina Center for Neurostimulation has run several trials similar to this, including a clinical trial assessing the use of tACS to treat depression over the course of a 5-day, 40-minute stimulation paradigm (Alexander et al., 2019).

This study is a critically necessary preliminary step in this line of research. The most important aspects of the study are its exploratory analyses, its provision of point- and interval-estimates of parameters of interest, and the logistical feasibility and tolerability information it will provide. The levels of precision of the estimators of interest are important; e.g., based on a previous tACS intervention study (Alexander et al., 2019) with a mean alpha oscillatory difference of ~ 2 and $SD \approx 1.2$ and alpha set at .05, we anticipate $N=20$ per group will provide more than 80% power. The effect size was based off the difference between active tACS and sham stimulation. This study will also provide an initial indication of whether it is plausible that tACS may have beneficial effects for the target lupus population. Based on the anticipated

precision of estimators, power levels of test procedures, availability of research subjects, and stage of this line of research, we believe the study is likely to achieve its specific aims; i.e., there is low risk the study will be uninformative/inconclusive.

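### Side-effect severity is summarised only by mean and SD, with no count of participants by worst severity in any arm

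*Combined protocol and SAP*

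**What the plan says.** Section 9.4.4 of the combined protocol and SAP says that the adverse effects questionnaire is "administered following every stimulation session, for a total of 5 administrations per participant" and "inquires about 14 possible adverse effects associated with electrical stimulation". Each item takes one of four ordered grades, from 1 (absent) to 4 (severe); the form itself is in section 6.1.2. The only descriptive summary is: "Severity per adverse effect will be described with mean and standard deviation". Counts and percentages are planned in the same section for verified suicidal ideation and verified mania, but not for these grades.

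Three other places bear on the point:

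- Section 9.4.1 assigns means and SDs to continuous data, and counts and percentages to categorical data.
- Section 9.2 says "The most important aspects of the study are its exploratory analyses", and continues the list to the "logistical feasibility and tolerability information it will provide".
- Section 9.3 defines one analysis population, those who complete all five days of stimulation. No separate safety population is defined there or in 9.4.4.

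**The concern.** The grades are ordered categories, and the tolerability question is about people: how many in each arm had a moderate or severe reaction? A mean of the codes 1 to 4 treats three mild ratings as equal to one severe rating, because each adds 3 to the total. Adding the SD does not restore the grade distribution. A reader of the planned table could not recover how many participants had any severe rating. Nor could the reader make the kind of statement that section 2.3.1 makes about the earlier trial, that effects were absent or mild in all groups.

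The single completers-only population makes this worse. A participant who has a bad reaction and does not finish the five days drops out of the summary altogether. For a pilot that offers tolerability as a main product, these are the cases that the next study would most need to see.

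**Working it through.** The plan gives no tolerability figure to reproduce, so the check is on what the planned summary can and cannot show.

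**Inputs**
- Grades 1 to 4 and five administrations: section 9.4.4.
- At least 45 evaluable participants, allocated 1:1:1: section 4.1. This gives 45/3 = 15 per arm and 15 × 5 = 75 ratings per item per arm.
- Grade distributions: assumed for illustration. The documents give none; section 2.3.1 gives no proportions for the earlier trial.

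**Formulas.** With S the sum of the ratings, Q the sum of their squares and n the number of ratings: mean = S/n, and SD = √[(Q − S²/n)/(n − 1)].

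**Step 1: same mean and SD, different worst grade**
- Pattern A, 72 absent + 3 moderate: S = 72 + 9 = 81; Q = 72 + 27 = 99.
- Pattern B, 71 absent + 3 mild + 1 severe: S = 71 + 6 + 4 = 81; Q = 71 + 12 + 16 = 99.
- Both: mean = 81/75 = 1.08; SD = √[(99 − 87.48)/74] = 0.395.

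If each non-absent rating comes from a different participant, the counts differ plainly. A has 3/15 moderate and none severe. B has 3/15 mild and 1/15 severe (6.7%).

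**Step 2: does this depend on pooling sessions?** It does not.
- If all non-absent ratings fall in one session and that session is summarised alone (n = 15), both patterns have S = 21 and Q = 39. The mean is 1.40 and the SD is √[(39 − 29.4)/14] = 0.828.
- If each participant's five ratings are averaged first, A has three participants at 1.4, and B has three at 1.2 and one at 1.6. Squared distances from 1 sum to 3 × 0.16 = 0.48 and to 3 × 0.04 + 0.36 = 0.48. Both give mean 1.08 and SD √[(0.48 − 15 × 0.08²)/14] = 0.166.

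**Step 3: size of the shift if sessions are pooled**
- One of 15 severe once: 1 + 3/75 = 1.04. Three of 15 mild once: also 1 + 3/75 = 1.04.
- Three of 15 (20%) severe once: (72 + 12)/75 = 1.12. Nine of 15 mild once: (66 + 18)/75 = 1.12. The SDs here do differ (0.592 and 0.327), but they do not tell a reader how many participants were affected.
- With 20 per arm (the figure in section 9.2) or 24 per arm (72/3), one severe rating gives 1 + 3/100 = 1.03 or 1 + 3/120 = 1.025.

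**Step 4: effect of the completers-only population.** Suppose one participant of 15 rates an item severe after session 1 and does not complete. Section 9.3 excludes that participant. If the other 14 rate it absent throughout, the reported mean is 1.00.

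**Step 5: what counts would show.** Exact (Clopper-Pearson) 95% limits for x of n are the 2.5% point of Beta(x, n − x + 1) and the 97.5% point of Beta(x + 1, n − x).
- 0/15: 0% (0 to 21.8%); the upper limit is 1 − 0.025^(1/15).
- 1/15: 6.7% (0.2 to 31.9%).
- 3/15: 20% (4.3 to 48.1%).

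**The case against.** The strongest case against is that the questionnaire mean is not the only evidence on tolerability. Adverse events are recorded on case report forms with severity and relationship (8.3.4), reasons for withdrawal are kept (7.2, 9.3), and retention is measured session by session (5.5). Persistent related events count towards suspension (7.4.2), and the monitoring board receives six-monthly descriptives (9.4.6). Means of short rating scales are also a common convention, and the raw grades are kept, so counts could be produced at reporting. A reader might therefore go too far in inferring that the trial cannot show tolerability at all. That is not supported: the limitation belongs to this summary, not to all the data. What remains is that none of those sources is a planned severity table by arm. The board reports are interim and blinded, retention counts attendance, and the persistence rule covers only events lasting 14 days or more.

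Three other inferences also go beyond the documents.

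- *That a severe rating is itself the trigger for stopping stimulation.* Section 2.3.1 says: "If participant is experiencing severe discomfort (as determined by the adverse effects questionnaire or by self-report), the stimulation will be immediately stopped". The trigger is severe discomfort, however ascertained. The form also includes items such as sleepiness and improved mood, and it is completed after the session.
- *That averaging hides a harm which a test on counts would detect.* For 3/15 against 0/15 ever severe, a two-sided Fisher exact test gives p = 2 × C(15,3)/C(30,3) = 2 × 455/4060 = 0.22, and the exact intervals overlap widely. Counts describe the data better; at this size they would not settle the comparison.
- *That the plan pools the five sessions, or that a poorly tolerated arm would necessarily look clean.* Pooling is the natural reading of a summary per effect with no session breakdown, but it is not stated. An arm with repeated moderate or severe effects would show a clearly raised mean.

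**Conclusion.** The point holds as a gap in the planned reporting. For an ordinal item, section 9.4.4 departs from the rule in 9.4.1 and leaves out the summary that would answer the tolerability question, namely participants by worst grade in each arm. The loss of information is a property of mean and SD. Patterns with and without a severe reaction can give identical values (1.08 and 0.395 over 75 ratings), whether sessions are pooled, taken singly or averaged within participant. The means of 1.04 and 1.12 rest on assumed grade patterns, 15 per arm and pooling; they illustrate the problem and do not forecast results. Restricting the summary to completers can remove the cases that matter most, so the population has to change along with the summary.

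The primary EEG analysis is unaffected. This is an inexpensive correction that should be made before unblinding, because section 9.2 presents tolerability as a main output.

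**What to change.** Add to section 9.4.4, for each questionnaire item and arm:

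- the number and percentage of participants by worst severity (absent, mild, moderate, severe) over all sessions received;
- the percentage with worst grade moderate or severe, with an exact 95% CI.

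Base both on all participants who received any stimulation, not only completers of all five days, and show the number of sessions received, since early stoppers contribute fewer ratings. State whether any mean and SD is by session or pooled, and keep it as a supplement. Show the improved-mood item apart from the unwanted effects.

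The cost is a few SAP sentences and one table shell. No new data are needed and trial conduct does not change. With about 15 per arm the intervals will be wide, and the table should be presented as descriptive.
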